14.5.3.3 Clinical Laboratory Assessments

Summary statistics will be presented for Baseline laboratory measurements, including hematology, chemistry, coagulation, and urinalysis. Normal ranges for the laboratory parameters will be provided by the laboratory which performed the assessments. All normal ranges will be standardized and results will be reported in standard units. The tables will include summary statistics for the Baseline assessments and the changes from Baseline to each subsequent timepoint of measurement. Shift tables will be generated for each laboratory parameter (except urinalysis), showing the transitions

Version 5

from Baseline assessment to normal (within normal range), low, or high value on each subsequent timepoint. A listing of subjects with abnormal laboratory assessments will be presented.

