In mid and high dose groups there were findings of grade 1 and grade 2 desirable effects, consistent with the test items mode of action, comprising histiocytic proliferation in liver, lung, and spleen, oval cell proliferation, and bone marrow hypercellularity. Adverse findings, in particular in the high dose group, included treatment related adverse hematology and chemistry, organs weights, gross pathology and histopathology including erythrophagoctosis in liver and spleen, increased hemosiderosis (greater than grade 1) in spleen, lymphoid depletion in spleen, endothelial hyperplasia in lungs and eyes, and glomerular hypercellularity in kidneys.

Version 5

In view of the results NOAEL for MIS416 when administered twice weekly for 4 weeks to New Zealand white rabbits by i.v. route is greater than 50 μ g/kg and less than 500 μ g/kg bodyweight under the test conditions and doses employed.

1.4.4 26 Week Repeat Dose Study

In this GLP repeat dose toxicity study, respective groups of 6 animals per sex per group were administered MIS416 intravenously once weekly for 26 weeks with doses of 0 ug (control), 20 ug, 200 ug or 1000 ug /kg. Following the treatment period, 2 animals per group were held for a 4 week recovery period.

At the lowest dose of 20 μ g/kg there were no deaths. Principal effects included minimal leukocyte infiltration into the choroid of the eye, minimal portal inflammation in the liver, with no effects on liver enzymes, minimal mixed leukocyte infiltration in the lung in 2/8 animals, and lymphoid hyperplasia of the spleen in one of eight animals. Absolute and relative spleen weights were increased as well.

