At the middle dose (200 μ g/kg) there was no mortality whereas at the high (1000 μ g/kg) dose three animals died or were sacrificed when observed to be in a moribund condition during the fourth and fifth month. Cause of death was attributed to cardiac myofibre degeneration and necrosis. This finding, or any cardiac findings, was not found in any other surviving animal at any dose. Additional effects seen at these doses included small but statistically significant reductions in red cell parameters, slight decrease in platelet counts, increased globulin values with a corresponding decrease in Albumin/Globulin (A/G) ratio, and decreased calcium (females only). Although occasional random increases in liver enzyme levels were seen in some animals, there was no clear nor consistent effect. Histopathological evaluation of tissues showed effects in the spleen (hyperplasia of the germinal center and hyperplasia of the red pulp), liver (portal inflammation, with necrosis and fibrosis at the high dose only), lung (mixed leukocyte infiltration), eye (mixed leukocyte infiltration of the choroid), and kidney (tubular degeneration and regeneration, glomerulopathy and heterophil infiltration in high dose animals only).

In conclusion, the intravenous administration of MIS416 to rabbits on a weekly basis resulted in toxicological effects at the high dose that included mortality (3/8 animals), generally mild clinical pathology findings and histopathological effects in the eye, heart, kidney, liver, lung and spleen. These findings had either resolved or showed advancing resolution at the end of the four-week recovery period. Some of these findings, except mortality, were noted at the middle dose. Effects noted at the lowest dose of 20 ug/kg/dose were substantially reduced in incidence, and were limited to minimal leukocyte infiltration in the eye, minimal portal inflammation in the liver (no effects on liver enzymes) and lymphoid hyperplasia in the spleen in 1/8 animals. Thus, the dose of 20 ug/kg/dose is considered the NOAEL for the administration of MIS416 weekly for 26 weeks.

Version 5

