5.2 Inclusion Criteria

- 1. At least 18 years of age.
- 2. Diagnosis of MS, by the McDonald criteria¹⁷. (See Appendix 1)
- 3. Chronic progressive MS (CPMS), defined as either primary progressive MS (PPMS) or secondary progressive MS (SPMS), per the criteria of the National Multiple Sclerosis Society (USA) Advisory Committee on Clinical Trials of New

Version 5

Agents in Multiple Sclerosis¹⁸. [NOTE: In the dose-confirmation phase, only subjects with SPMS may be enrolled].

- 4. MS is clinically active with worsening clinical status within the past 2 years.
- 5. Expanded Disability Status Scale (EDSS) of 2.5 to 7.0 at Screening.
- 6. The following laboratory values must be documented within 3 days prior to initiation of study drug:
 - Absolute neutrophil count (ANC) \geq 1 x 10⁹/L
 - Platelet count $\geq 100 \times 10^9/L$
 - Serum creatinine \leq 1.5 mg/dL
 - AST (SGOT) and ALT (SGPT) $\leq 2 \times$ upper limit of normal.
- 7. Provide written informed consent to participate.
- 8. Willing to comply with scheduled visits, treatment plans, laboratory assessments, and other study-related procedures.

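### The laboratory shift tables in section 14.5.3.3 show direction but not severity of worsening, and leave out urinalysis; a baseline-to-worst shift would close the gap

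*Protocol*

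**What the plan says.** **Shift tables.** Section 14.5.3.3 states: "Shift tables will be generated for each laboratory parameter (except urinalysis), showing the transitions" "from Baseline assessment to normal (within normal range), low, or high value on each subsequent timepoint". There are three classes, set by the laboratory's normal range, and one panel is expressly left out.

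**Other laboratory displays in the same section.** "The tables will include summary statistics for the Baseline assessments and the changes from Baseline to each subsequent timepoint of measurement". Also: "A listing of subjects with abnormal laboratory assessments will be presented". Section 14.4.1 defines summary statistics to include the minimum, median and maximum for continuous variables and frequencies for categorical ones, by dose cohort.

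**Entry limits.** The criterion 6 line that begins "AST (SGOT) and ALT (SGPT" sets a ceiling of twice the upper limit of normal.

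**Unscheduled values.** Section 14.3.1.1 lists them but keeps them out of tabulations by visit. Section 12.2.7 asks for unexplained, clinically relevant abnormal results to be repeated at once.

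**Animal findings.** In the 4-week rabbit study (1.4.3): "glomerular hypercellularity in kidneys". In the 26-week rabbit study (1.4.4): "liver (portal inflammation, with necrosis and fibrosis at the high dose only" and "kidney (tubular degeneration and regeneration, glomerulopathy and heterophil infiltration in high dose animals only".

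**Synopsis.** The safety analysis paragraph says laboratory parameters will be summarised by descriptive statistics, post-dosing shifts from baseline, and listings. It makes no exception for urinalysis.

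**Endpoint.** The synopsis and section 7 both count effects on laboratory parameters within the primary safety endpoint.

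**The concern.** A shift table is the usual place to read how many subjects at each dose level moved, and from what starting point. Here it can register only a crossing of the normal limit. For a parameter on which the protocol admits abnormal baselines, a subject can deteriorate markedly without leaving the starting class, while a trivial crossing of the limit is counted.

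Urinalysis, which includes protein and red cells, is the only panel without a shift table, yet the kidney is one of the organs affected in the rabbit studies. At stake is the summary of a primary safety endpoint by dose level, in a trial meant to select a dose and build a safety database for a longer trial.

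**Working it through.** No figure in the plan bears on this point, so there is none to reproduce. The check applies the stated rule to example values and then sets the relevant sections side by side.

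**1. The three-class rule applied to AST/ALT.** Inputs: the classes from 14.5.3.3 and the entry ceiling of 2 × ULN from criterion 6. The baseline and later values are assumptions, in multiples of ULN. Rule: x > 1 is high; x ≤ 1 (and not low) is normal. A shift is shown only if the class changes.

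| Baseline | Later values tried | Cell | Shift shown? |
|---|---|---|---|
| 0.8 | 1.2, 2, 3, 5, 10 | normal to high | yes, all in one cell |
| 1.0 | 1.2, 2, 3, 5, 10 | normal to high | yes, all in one cell |
| 1.2 | 2, 3, 5, 10 | high to high | no |
| 1.5 | 2, 3, 5, 10 | high to high | no |
| 2.0 | 3, 5, 10 | high to high | no |

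A move from 1.0 to 1.2 (change 1.2 − 1.0 = 0.2 × ULN) is a shift. A move from 2.0 to 10 (change 10 − 2.0 = 8.0 × ULN) is not.

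**2. What the change-from-baseline table recovers.** It gives the maximum change per cohort and visit. A subject going from 1.8 to 8 × ULN appears there as 8 − 1.8 = 6.2. A subject going from 0.8 to 7.0 also gives 7.0 − 0.8 = 6.2. The maximum therefore reveals that a large rise occurred, but not from which baseline, to what level, or in how many subjects.

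**3. Unscheduled values.** Sections 12.2.7 and 14.3.1.1 together mean that a peak found at an unscheduled repeat is listed but enters no by-visit table. Because 14.5.3.3 defines shifts by timepoint, there is no worst-value table to catch it.

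**4. Laboratory values as adverse events.** Section 12.2.1 lets a clinically significant laboratory abnormality be an adverse event. Section 12.2.3 keeps other laboratory abnormalities off the adverse event page unless they lead to a clinically relevant condition. Those that are reported reach the Grade 1–4 table in 14.5.3.2, without their baseline class. In the dose-escalation phase a laboratory abnormality can also be a DLT (4.4). That definition does not extend to the dose-confirmation phase.

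**5. Urinalysis.** Protein and red cells are collected (7.4). Section 14.5.3.3 includes urinalysis in the baseline and change summaries but not in the shift tables. The synopsis states laboratory shifts without that exception, so the two texts differ.

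**6. Weight of one subject.** Escalation levels hold 3 or 6 subjects: 1/3 = 33% and 1/6 = 17%. In a dose-confirmation cohort of 15, one subject is 1/15 = 6.7%.

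**The case against.** The strongest reply is that this concerns display and not loss of information. The summary statistics include the maximum as well as the mean. Categorical urine results can be given as frequencies by cohort. Creatinine and urea are chemistry parameters and keep their shift tables. Clinically significant laboratory abnormalities can be graded adverse events. With about 27–33 subjects, the listing shows each abnormal case. The Safety Review Team works from all available clinical safety and PD data, and no hypothesis test depends on these tables. The animal evidence is also qualified: the 26-week study found no clear or consistent liver-enzyme effect, and its kidney findings were confined to the high dose.

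All of that stands, and it rules out several stronger readings that a reader might reach:

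- That worsening liver tests in general show no shift. This is true only for a baseline already above ULN.
- That mean change is the only other table. Maxima and frequencies are planned too.
- That graded laboratory toxicity is tabulated nowhere. The graded adverse event table holds the abnormalities reported as events.
- That a kidney signal could appear only in a listing. Creatinine and urea shifts and urinalysis summaries remain.

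It could also be said that table design belongs in the SAP, which is not at hand. That would be right had the protocol been silent. Here the protocol itself fixes the three classes and the urinalysis exclusion, and its synopsis does not match.

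The reply does not supply a display that counts subjects by baseline class and severity of worsening at each dose level. Listings give no incidence, maxima give no counts, frequencies at a visit do not link a subject to baseline, and the adverse event table depends on a judgement of clinical relevance.

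**Conclusion.** The point holds as a weakness in how the laboratory tables are specified, worth correcting because it is cheap. It is not an error of figures, and no safety data are lost.

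Three features of the stated rule combine. Worsening from a baseline above 1 and up to 2 × ULN is shown as no change of class. Worsening from normal is shown without its size. Peaks at unscheduled repeats are left out of by-visit tables. Separately, urine protein and red cells have no shift table, and section 14.5.3.3 and the synopsis do not agree on this.

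The size cannot be stated more closely than one subject being 17% to 33% of an escalation level. The documents do not say how many subjects will enter with raised AST/ALT, and the values in the worked table are illustrative. The same masking would affect neutrophils and platelets only if the laboratory's lower limits lie above the entry floors of 1 and 100 × 10⁹/L, and no normal ranges are given.

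**What to change.** In section 14.5.3.3:

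- Add, by dose level, a shift from baseline to worst post-baseline value, with unscheduled values included. Classify by the toxicity grade the protocol already uses, or by multiples of ULN or LLN where that scale has no entry. Cover at least AST/ALT and the other key safety parameters. The full scale sits in the Operations Manual, so check its coverage parameter by parameter.
- Add a baseline-to-worst category shift for urine protein and red cells.
- Reconcile the urinalysis exclusion with the synopsis.

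The existing low/normal/high tables, change summaries and listings can stay. The cost is wording, some programming and a few more tables. The data are already collected, and no visit, dosing or management rule is affected.

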14.5.3.4 Vital Signs

Vital signs, including changes from baseline to each subsequent timepoint, will be summarized for each dose level using descriptive statistics.

14.5.3.5 Electrocardiogram (ECG) Findings

ECG findings, including changes from baseline to each subsequent timepoint, will be summarized for each dose level using descriptive statistics. The number and percentage of subjects with clinically significant abnormal ECG findings at any visit will be tabulated.

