6.2.1 DE Phase Subjects

DE phase subjects will be admitted to the unit for pre-study safety blood, PD and immune parameter analysis and urine testing, pregnancy testing (if applicable), weight, vital signs, ECG and EDSS on Day 1

Subjects will undergo a physical examination (including neurological) and vital signs. Any medical history and concomitant medications taken since screening will be recorded and eligibility confirmed.

An indwelling intravenous cannula will be sited in a forearm.

A light breakfast will be consumed approximately 30 minutes prior to the scheduled dosing time.

Study drug will be drawn up in accordance with instructions in the Operations Manual and administered at the scheduled time by a slow intravenous infusion over 10 minutes. Subjects will be closely monitored for changes in their health or physiological status. At any time during dosing, the infusion rate can be reduced or the infusion turned off in response to an adverse event occurring. Once the infusion is completed, the cannula will be flushed with 0.9% sodium chloride for injection. The cannula will stay *in situ* until discharge on Day 2.

Subjects will be required to remain in bed for four hours post dose and then will be allowed to mobilise gently around the unit.

Vital signs will be repeated mid-way through the infusion (5 mins), 15 and 30 minutes, 2,4, 6, 8, 10, 12, 16, 20 and 24 hours post-dose. ECGs will be repeated 30 minutes, 1, 2, 4, 6, 8, 12 and 24 hours post-dose. Adverse event enquiry will be completed mid-way through the infusion (5 mins), 15 and 30 minutes, 2, 4, 6, 8, 10, 12, 16, 20 and 24 hours post dose and ongoing throughout the inpatient stay.

Meals, snacks and drinks will be provided throughout the day and subjects will remain overnight on the unit.

A 24-hour post-dose blood sample for PD and immune parameter sampling will be obtained the morning of Day 2 by venesection (**not via the indwelling cannula**). The cannula can be removed and the subject discharged from the unit if well.

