6.2.2 DC Phase Subjects

DC phase subjects will undergo the identical procedures, and in addition will undergo a screening ophthalmologic examination to consist of visual acuity determination, biomicroscopy, and dilated fundoscopy; and testing for MSFC, FSS, and SF-36.

6.3 Treatment Period (Cycle 1) – Days 8, 15 and 22 (± 1) – All Subjects

All DE and DC phase subjects will be admitted to the unit the morning of dosing for a brief physical examination (including neurological examination and EDSS where clinically indicated), and vital signs, ECG, weight (Day 22 only) and pregnancy testing if applicable (Day 22 only). Any adverse events and concomitant medications taken since the last visit will be recorded and eligibility confirmed.

An indwelling intravenous cannula will be sited in a forearm. A pre-dose blood sample will be taken for safety samples, PD and immune parameter analysis.

Study drug will be administered at the scheduled time by a slow intravenous infusion over 10 minutes. Subjects will be closely monitored for changes in their health or physiological status. At any time during dosing, the infusion rate can be reduced or turned off in response to an adverse event occurring. Once the infusion is completed, the cannula will be flushed with 0.9% sodium chloride for injection. The cannula will stay *in situ* until discharge.

Subjects will be required to remain in bed for four hours post dose and then will be allowed to mobilise gently around the unit.

Vital signs will be repeated mid-way through the infusion (5mins), 15 and 30 minutes, 2 and 4 hours post-dose. ECGs will be repeated 30 minutes, 1, 2 and 4 hours post-dose. Adverse event enquiry will be completed mid-way through the infusion, 15 and 30 minutes post dose and ongoing throughout the inpatient stay.

Meals, snacks and drinks will be provided throughout the day.

Subjects will be discharged mid afternoon but may remain in the unit for up to 24 hours at the discretion of the Investigator.

Subjects will return the following morning for a 24-hour post-dose blood sample for PD and immune parameter blood sampling.

6.4 Treatment Period (Cycles 2 – 3) – Days 1, 8, 15 and 22 (+ 1) – DC Phase Subjects Only

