DC phase subjects will be admitted to the unit the morning of dosing for a brief physical examination (Day 1 only), weight (Day 1 and Day 22), ECG and vital signs. Any adverse events and concomitant medications taken since the last visit will be recorded and eligibility confirmed. An MSFC, FSS, and EDSS will be performed on Day 1 of each cycle, and the SF-36 will be performed at the end of Cycle 3 only. An ophthalmologic examination, to consist of visual acuity determination, biomicroscopy, and dilated fundoscopy, will be performed within a week of the end of Cycle 3. (EDSS will be repeated following neurological examination at any visit where indicated by a change in functional status).

A cranial MRI will be performed at the end of Cycle 3 (details to be provided in the companion Radiology Manual of Operations).

An indwelling intravenous cannula will be sited in a forearm. A pre-dose blood sample will be taken for safety samples (Days 8 and 22 in Cycles 2 and 3, and End of Dosing or Early Discontinuation where applicable). A pre-dose blood sample for PD and immune parameter analysis will be taken on Day 22 of each cycle.

Version 5

Study drug will be drawn up and administered at the scheduled time by a slow intravenous infusion over 10 minutes. Subjects will be closely monitored for changes in their health or physiological status. At any time during dosing, the infusion rate can be reduced or turned off in response to an adverse event occurring. Once the infusion is completed, the cannula will be flushed with 0.9% sodium chloride for injection. The cannula will stay *in situ* until discharge.

Subjects will be required to remain in bed for four hours post dose and then will be allowed to mobilise gently around the unit.

Vital signs will be repeated mid-way through the infusion (5 mins), 15 and 30 minutes, 2 and 4 hours post-dose. ECG will be repeated at 4 hours post-dose. Adverse event enquiry will be completed mid-way through the infusion, 15 and 30 minutes post dose and ongoing throughout the inpatient stay.

Meals, snacks and drinks will be provided throughout the day.

Subjects will be discharged mid afternoon but may remain in the unit for up to 24 hours at the discretion of the Investigator.

6.5 Treatment Period -End of Dosing (Day 29) or Early Discharge-(7 +1 days following last dose of drug)

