7.6 ECG and Echocardiogram

A 12-lead ECG will be recorded for all subjects at screening, pre-dose and 30 minutes, 1, 2 and 4 hours (and 6, 8, 12 and 24 hours on Day 1) post-dose in Cycle 1, at the end of study dosing, and at follow up. For DC phase subjects only, ECG will be recorded predose and 4 hours post dose on each subsequent dosing day.

An ECG will be recorded after the subject has been lying supine for at least 5 minutes. The date and time the ECG was recorded, as well as the protocol and subject identification details should be recorded on the printout.

The following parameters will be recorded in the CRF: heart rate, PR, QRS, QT, QT_{cF} as well as any abnormality in rhythm or wave morphology.

In the DC phase only, subjects will undergo echocardiography during screening.

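### The any-visit ECG abnormality percentage in Section 14.5.3.5 sets DC subjects (12 doses, 41 ECGs) beside DE subjects (4 doses, 25 ECGs), so the RP2D figure is not comparable with the other dose levels

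*Protocol*

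**What the plan says.** All references are to the protocol.

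- **Analysis.** Section 14.5.3.5 plans two ECG summaries. The first gives ECG findings and changes from baseline at each later timepoint, by dose level. The second is a subject-level rate: "The number and percentage of subjects with clinically significant abnormal ECG findings at any visit will be tabulated". That sentence does not mention dose level, but Section 14.4.1 has the data for all subjects tabulated by dose cohort and for the whole population. Neither section gives a common observation window, a split by phase or an allowance for the number of ECGs.
- **Dose 1.** Section 6.2.1 (DE): "ECGs will be repeated 30 minutes, 1, 2, 4, 6, 8, 12 and 24 hours post-dose". Section 6.2.2 extends this to DC: "DC phase subjects will undergo the identical procedures".
- **Doses 2 to 4, all subjects.** Section 6.3: "ECGs will be repeated 30 minutes, 1, 2 and 4 hours post-dose".
- **Doses 5 to 12, DC only.** Section 6.4: "ECG will be repeated at 4 hours post-dose".
- **Cross-check.** Section 7.6 gives the same schedule: "pre-dose and 30 minutes, 1, 2 and 4 hours (and 6, 8, 12 and 24 hours on Day 1) post-dose in Cycle 1", with further ECGs at end of dosing and at follow-up, and then "For DC phase subjects only, ECG will be recorded predose and 4 hours post dose on each subsequent dosing day".
- **Dose in the DC phase.** Section 4.5 recruits up to 15 DC subjects, all at the RP2D.

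**The concern.** A subject enters the any-visit numerator if a single ECG is abnormal, so the chance of being counted rises with the number of ECGs and the time on drug. Both differ by phase, and the DC phase sits at one dose level. When the table is laid out by dose cohort, one column has been observed for three cycles and the others for one. A higher percentage in that column could reflect dose, longer exposure or more recordings, and the table cannot separate them.

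ECG is the cardiac test that is repeated during dosing; Section 7.6 schedules echocardiography at screening only, and only for DC subjects. Section 1.4.4 reports deaths at the high dose in the 26-week rabbit study: "Cause of death was attributed to cardiac myofibre degeneration and necrosis". Readers will therefore look at the ECG table closely, and the any-visit percentage is the one subject-level ECG abnormality rate that the section names. It should compare like with like.

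The wording also does not confine the count to ECGs after the first dose, so a finding at screening or before dosing on Day 1 could be counted.

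**Working it through.** **Step 1: scheduled ECGs per completer, after the first dose has been given**

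| Component | DE (4 doses) | DC (12 doses) |
|---|---|---|
| Post-dose, dose 1 | 8 | 8 |
| Post-dose, doses 2–4 | 3 × 4 = 12 | 3 × 4 = 12 |
| Post-dose, doses 5–12 | none | 8 × 1 = 8 |
| **Post-dose subtotal** | **20** | **28** |
| Later pre-dose ECGs | 3 | 11 |
| End of dosing and follow-up | 2 | 2 |
| **Total** | **25** | **41** |

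Ratios: 41/25 = 1.64 for all ECGs after first dosing; 28/20 = 1.40 for post-dose ECGs only. Across the DE dose levels the ratio is 1.00.

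**Step 2: effect on an any-visit percentage when the drug has no effect**

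The protocol gives no per-ECG rate. Assume a constant probability p, independent between ECGs. The expected percentage is 1 − (1 − p)^n.

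| p per ECG (assumed) | DE, n = 25 | DC, n = 41 |
|---|---|---|
| 0.1% | 2.5% | 4.0% |
| 0.5% | 11.8% | 18.6% |
| 1% | 22.2% | 33.8% |
| 2% | 39.7% | 56.3% |

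**Step 3: sensitivity to independence**

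ECGs from one person on one day are unlikely to be independent. At the other extreme, let findings cluster completely within a visit. From Day 1, DE has 4 + 2 = 6 visits and DC has 12 + 2 = 14. At an assumed 1% per visit, 1 − 0.99^6 = 5.9% and 1 − 0.99^14 = 13.1%. The absolute figures fall, but the imbalance stays: 14/6 = 2.33 in visits.

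**Step 4: pooling**

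The protocol does not say whether DC subjects form their own column or join the DE subjects treated at the same dose. With p = 1%, independence and 15 DC completers:

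- pooled with 3 DE subjects: (3 × 22.2% + 15 × 33.8%)/18 = 31.8%;
- pooled with 6 DE subjects: (6 × 22.2% + 15 × 33.8%)/21 = 30.5%.

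Either way the RP2D column stays well above the 22.2% expected elsewhere. The total-population percentage, with the planned 12 to 18 DE subjects, would be (12 × 22.2% + 15 × 33.8%)/27 = 28.6% or (18 × 22.2% + 15 × 33.8%)/33 = 27.5%. It describes neither schedule.

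**Step 5: early withdrawal within DE**

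Section 4.3 withdraws any DE subject who has a DLT. After 1, 2, 3 or 4 doses a subject has 8, 12, 16 or 20 post-dose ECGs. A subject withdrawn after dose 1 who attends the early-discharge and follow-up visits has 8 + 2 = 10 ECGs instead of 25. At p = 1% that is 1 − 0.99^10 = 9.6% against 22.2%. This is the only route by which the schedule disturbs the comparison among DE levels.

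**The case against.** There is a good deal to say for the plan as it stands.

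- **The DE dose comparison is sound.** Every DE level has the same schedule, so a reader who infers that the rate follows the number of ECGs rather than dose or exposure goes too far. DC subjects have more ECGs because they receive more doses. ECG count is confounded with exposure and does not replace it. This stands, subject to Step 5.
- **No late signal is hidden by this table.** One might infer from the thinning schedule (8, then 4, then 1 post-dose ECGs per dose) that abnormalities would seem to decline over cycles. That would need a rate by cycle, and Section 14.5.3.5 plans none. A late abnormality still counts in an any-visit total. The rabbit deaths came in the fourth and fifth months at the highest dose only, beyond three 28-day cycles, and the protocol does not say that ECG changes preceded them. This stands too.
- **The same section plans summaries by timepoint and dose level.** The number of ECGs does not inflate those. They soften the problem but leave the any-visit percentage uncorrected.
- **No decision depends on it.** Under Sections 4.3 and 4.5 the RP2D is fixed before DC subjects are recruited, and Section 14.4.2 rules out formal testing. With 3 to 6 subjects per DE cohort and up to 15 in DC, the percentages are coarse. This limits the severity. A descriptive rate is still what readers will compare across columns.
- **It may be a matter for the SAP.** Table layouts often are. Here, however, the protocol itself names the summary and, through Section 14.4.1, its columns.

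**Conclusion.** The point holds in a limited form and is of low severity. The any-visit percentage for DC, or for the RP2D with DC subjects included, is not comparable with the other dose levels: it rests on up to 12 doses and 41 scheduled ECGs against 4 doses and 25. The total mixes both schedules. Among DE levels the comparison is fair apart from early withdrawal.

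The ECG counts come straight from the protocol and assume that subjects complete dosing and both closing visits. The percentages are illustrations only. They rest on an assumed constant, independent per-ECG probability of 0.1% to 2%, and clustering within visits would change them. The documents do not support the stronger readings that the rate is unrelated to dose or exposure, or that the table would conceal a late cardiac effect.

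**What to change.** Amend Section 14.5.3.5 as follows.

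1. Keep the any-visit count and percentage, but report it separately for DE and DC, with the number of ECGs per subject alongside.
2. State that only ECGs after the first dose are counted.
3. For the comparison of dose levels, add the percentage of subjects with any clinically significant abnormality in Cycle 1, by dose level. From the first post-dose ECG on Day 1 to the last scheduled ECG on Day 22, all subjects share one schedule of 8 + 3 × (1 + 4) = 23 ECGs. Showing ECGs per subject makes any shortfall from early withdrawal visible.
4. If a trend over Cycles 1 to 3 is described for DC subjects, use only the pre-dose and 4-hour ECGs, which are recorded at every dose, with the Day 1 pre-dose ECG serving as baseline.

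The cost is table programming. No ECG, visit or procedure is added, and no planned summary is lost.
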